**MS Bowel Study** 

T1.0 Select the type of application:

New Research Study

T2.0 Is the proposed research study limited to the inclusion of deceased individuals?

\* No

T2.1 Are any research activities being conducted at the VA Pittsburgh Healthcare

System or with VA funds?

\* No

[reviewer notes¬]

T3.0 What is the anticipated risk to the research participants?

Greater Than Minimal Risk

Section: Cover Sheet

[reviewer notes-]

CS1.0 What is the reason for this submission?

New Research Protocol Submission

CS1.1 Has this research study been approved previously by the University of Pittsburgh IRB?

\* No

# CS1.1.1 Has this research study (or a substantially similar research study) been previously disapproved by the University of Pittsburgh IRB or, to your knowledge, by any other IRB?

\* No

[reviewer notes¬]

### CS2.0 Title of Research Study:

**Treating Anorectal Dysfunction Associated with Multiple Sclerosis** 

### CS2.0.1

Requested approval letter wording:

#### CS2.1 Research Protocol Abstract:

The majority of patients with multiple sclerosis (MS) suffer from constipation and/or fecal incontinence ("anorectal dysfunction"), and these difficulties are often ranked as negatively impactful on quality of life as impaired mobility. Despite the significant clinical burden of these symptoms, there remains very little research to support specific therapeutic options in managing anorectal dysfunction in MS patients. To address this gap in knowledge, we propose to establish the efficacy of a standardized, cost-effective, and easily implemented bowel regimen to treat anorectal dysfunction in patients with MS.

Specifically, this double-blind, randomized placebo controlled study will determine the impact of adding the regular administration of rectal suppository laxatives (e.g., a "timed rectal evacuation" strategy) on MS patients' subjective assessment of bowel symptoms. The "timed rectal evacuation" aspect of a bowel regimen has never been rigorously studied, but it could have a major clinical impact. In our study, patients with MS will receive oral laxatives or anti-diarrheal agents to normalize stool form (as indicated), and then be randomized to receive either placebo or bisacodyl 10 mg rectal suppositories administered every other day for 4 weeks. Patients also will undergo tests of anorectal function (per routine clinical practice) and standardized questionnaire assessments of bowel symptoms and their impact on quality of life. We will use this information to try to predict which groups of patients benefitted from the intervention. This proposal will significantly advance MS care and management by developing the evidence to support a simple and effective clinical treatment algorithm for anorectal dysfunction in the MS population.

### **CS2.2** Select the category that best describes your research:

[reviewer notes-]

CS9.0 Does this research study involve the administration of an investigational drug or an FDA-approved drug that will be used for research purposes?

### CS9.1 Do you plan to utilize the Investigational Drug Service (IDS) to dispense the drug?

\* Yes

# CS10.0 Is this research study being conducted under a University of Pittsburgh-based, sponsor-investigator IND or IDE application?

\* No

If YES, you are required to submit the IND or IDE application and all subsequent FDA correspondence through the Office for Investigator-Sponsored IND and IDE Support (O3IS). Refer to applicable University policies posted on the O3IS website (www.O3IS.pitt.edu).

[reviewer notes-]

### CS11.0 Use the 'Add' button to upload one or more of the following:

- the sponsor protocol (including investigator initiated studies) and/or other brochures
- the multi-center protocol and consent form template, if applicable

Name Modified Date

Is this research study supported in whole or in part by industry? This includes the provision of products (drugs or devices).

\* No

Is this a multi-centered study?

\* No

[reviewer notes-]

- CS12.0 Does your research protocol involve the evaluation or use of procedures that emit ionizing radiation?
  - \* No
- CS13.0 Does this research study involve the deliberate transfer of recombinant or synthetic nucleic acid molecules into human subjects?
  - \* No

Upload Appendix M of NIH Guidelines:

Name Modified Date

CS14.0 Are you using UPMC facilities and/or UPMC patients during the conduct of your research study?

\* Yes

If Yes, upload completed Research Fiscal Review Form:

Name Modified Date

FRIAR - OSPARS Form -- [name] 2015.docx

11/3/2015 3:01 PM

[reviewer notes-]

# CS15.0 Indicate the sites where research activities will be performed and/or private information will be obtained.

Choose all sites that apply and/or use **Other** to include sites not listed:

Sites:

**UPMC** 

UPMC
Sites:
UPMC Presbyterian
UPMC Montefiore
Other UPMC Site- Specify below:

Kaufman Building (Department of Neurology outpatient suite)

If you selected **School**, **International** or **Other**, list the sites:

\*For research being conducted at non Pitt or UPMC sites, upload a site permission letter granting the researcher permission to conduct their research at each external site:

Name Modified Date

- CS15.1 Have you, [name], verified that all members of the research team have the appropriate expertise, credentials, and if applicable, hospital privileges to perform those research procedures that are their responsibility as outlined in the IRB protocol?
  - \* Yes
- CS15.2 Describe the availability of resources and the adequacy of the facilities to conduct this study:
  - \* Our study enrolls patient subjects that are already embedded within existing clinical care pathways at UPMC. Patients with multiple sclerosis (MS) already receive care in the Division of Neuroimmunology/MS in the Department of Neurology at UPMC, who maintains a large (2000+patients) database of their MS patients with associated clinical data. Importantly, the registry also records information on patients' expressed

interest in participating in clinical research studies. During routine care, MS patients with anorectal dysfunction are already regularly referred to the Neurogastroenterology and Motility Group (PI and co-PI) within the Digestive Disorder Center at UPMC and undergo anorectal manometry testing and treatment in the DDC. We will use both routine care pathways and the MS database to recruit patients into the study (goal: 70 patients). We have contracted with Hieber's pharmacy and Falk Pharmacy to forumulate and distribute the study drug in a blinded fashion. We are currently in the process of identifying a study coordinator. The funding mechanism for this project has ample resources to support both of these efforts (study drug and coordinator). Thus, all of the resources that are required to conduct this study are easily available and fully adequate.

[reviewer notes¬]

# **CS16.0** Special Research Subject Populations:

Categories

None

[reviewer notes¬]

### CS17.0 Does your research involve the experimental use of any type of human stem cell?

\* No

[reviewer notes¬]

### **NIH Definition of a Clinical Trial**

A research study in which one or more human subjects are prospectively assigned to one or more interventions (which may include placebo or other control) to evaluate the effects of those interventions on health related biomedical or behavioral outcomes.

-  See Common Rule definition of research at 45 CFR 46.102(d) .
-  See Common Rule definition of human subject at 45 CFR 46.102(f) .
-  The term "prospectively assigned" refers to a pre-defined process (e.g., randomization) specified in an approved protocol that stipulates the assignment of research subjects (individually or in clusters) to one or more arms (e.g., intervention, placebo, or other control) of a clinical trial.
-  An intervention is defined as a manipulation of the subject or subject's environment for the purpose of modifying one or more health-related biomedical or behavioral processes and/or endpoints. Examples include: drugs/small molecules/compounds; biologics; devices; procedures (e.g., surgical techniques); delivery systems (e.g., telemedicine, face-to-face interviews); strategies to change health-related behavior (e.g., diet, cognitive therapy, exercise, development of new habits); treatment strategies; prevention strategies; and, diagnostic strategies.

 Health-related biomedical or behavioral outcome is defined as the pre-specified goal(s) or condition(s) that reflect the effect of one or more interventions on human subjects' biomedical or behavioral status or quality of life. Examples include: positive or negative changes to physiological or biological parameters (e.g., improvement of lung capacity, gene expression); positive or negative changes to psychological or neurodevelopmental parameters (e.g., mood management intervention for smokers; reading comprehension and /or information retention); positive or negative changes to disease processes; positive or negative changes to health-related behaviors; and, positive or negative changes to quality of life.

# CS18.0 \* Based on the above information, does this study meet the NIH definition of a clinical trial?

Yes	0	No
-----	---	----

If Yes, click Save and then Click Here For Study Team's CITI Training Records. Please ensure all personnel's training is up to date

Section: Section 1 - Objective, Aims, Background and Significance

[reviewer notes¬]

# **1.1 Objective: What is the overall purpose of this research study?** (Limit response to 1-2 sentences.)

The goal of this proposal is to determine the impact of adding timed rectal evacuation as a treatment for anorectal dysfunction symptoms in patients with mild-to-moderate severe MS.

# 1.2 Specific Aims: List the goals of the proposed study (e.g., describe the relevant hypotheses or the specific problems or issues that will be addressed by the study).

MS-related disability and impaired quality of life is derived from both motor and non-motor symptoms associated with the disease. One of the most common, chronic non-motor symptoms in MS patients is anorectal dysfunction, broadly defined as the presence of chronic constipation and/or fecal incontinence. Anorectal dysfunction is experienced in some form by a majority of MS patients and is likely driven by subtle impairments in sensorimotor function that undermines patients' ability to sense rectal filling and/or appropriately coordinate pelvic muscles required for normal defecation. Collectively, because of the pervasive presence of common symptoms with a daily impact, anorectal dysfunction places a tremendous burden on MS patients and their caregivers. Yet, there is exceptionally little high quality evidence to suggest a specific therapeutic approach to MS patients with anorectal dysfunction. Thus, there is a compelling need to establish the evidence to support a safe, effective, and easily implemented treatment option for anorectal dysfunction in MS patients. As a first step to meeting this need, this proposal aims to determine the efficacy of timed rectal evacuation in an algorithm-based bowel regimen for treating anorectal dysfunction in patients with mild-to-moderate severity MS.

# AIM 1: Determine the impact of timed rectal evacuation on anorectal dysfunction in MS patients

We will conduct a four week, single-center, randomized, double-blind placebo controlled clinical trial designed to assess the efficacy of timed rectal evacuation in improving the subjective global assessment of bowel symptoms in a cohort of patients with mild-to-moderate severity MS disease. Patients will be randomized 1:1 to administer either placebo or bisacodyl 10 mg rectal suppositories every other day during the 4 week trial. The primary endpoint will be the change in patients' rating of bowel symptom severity (10 point rating scale) at end of 4 weeks compared to baseline values. We will define an adequate treatment response as greater than a 30% reduction in symptom severity using an intention-to-treat analysis.

AIM 2: Determine the predictors of treatment response and impacts on quality of life

We plan to collect information on the patients' assessed severity of baseline and treatment-associated anorectal dysfunction, their impact on quality of life, as well as daily bowel diaries. Patients also will undergo anorectal sensory and manometric testing as a part of their routine clinical care. Enrolled patients that complete the study will be assessed for study medication compliance. All of these measures will be used to explore factors that are associated with treatment response. Changes in assessments of anorectal dysfunction-related quality of life will serve as key secondary end-points.

This proposal will significantly advance MS care and management by developing the evidence to support the adoption of a simple, safe, and cost-effective clinical treatment algorithm for anorectal dysfunction in the MS population. This paradigm for anorectal dysfunction management could be applicable to a majority of MS patients, and the treatment algorithm could be introduced to patients by nurses or mid-level clinical providers during points of routine MS patient care. Importantly, the treatment could be effectively accomplished by most patients and their caregivers at home. The findings of this investigation could also have a broader influence on care models for anorectal dysfunction associated with a range of other neurological illnesses, such as Parkinson's Disease, ALS, or stroke.

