Study flow: A schematic of the study flow is shown in the attached figure. All patient encounters, referrals, and tests are integrated into the flow of routine clinical care at UPMC. Recruited patients will meet with the study coordinator in an in-person meeting to discuss the details of the study and obtain informed consent (Kaufman Building MS Clinic). At that time (Phase 1), additional measures of baseline bowel symptom severity and bowel-related quality of life (QOL) will be obtained by standardized questionnaires (see below). The study coordinator will provide patients with instructions on maintaining a daily bowel diary (see Study Measures below), and then initiate referrals for anorectal function testing in the DDC and a later follow-up appointment with the PI/Co-PI ("NeuroGI"). The consent process, baseline questionnaires, and instructions on bowel diary are unlikely to take more than 1 hour of time.

During the next 2-4 weeks after study entry, patients will complete the baseline daily bowel diary.

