Finally in Phase 3, after the 4 week study period, patients will meet with the study coordinator to collect unused study medication and completed bowel diaries, and then undergo final reassessments of bowel dysfunction severity and QOL measures. This process could take up to 1 hour. After the questionnaires are completed, patients and the PI/Co-PI will be debriefed (i.e. study arm allocation will be revealed) before having a routine followup clinic visit (continuity of care).

- 1) The study coordinator will identify and screen potential study subjects (by accessing the "UPMC Multiple Sclerosis and Related Disorders Registry" (PRO12010609) to identify prospective subjects), coordinate the informed consent process with the PI/Co-PI, collect intake questionnaires, and provide instruction on bowel diaries (Phase 1). The coordinator will schedule referrals for anorectal function testing and follow-up DDC visit, and contact patients during the 4-week trial period to verify compliance. Finally, the coordinator will collect bowel diaries and remaining medications at study end, administer study exit questionnaires, and then debrief subjects and the PI/Co-PI once the blind is broken (Phase 3).
- 2) DDC GI nursing staff routinely performs HRAM studies and will do so in this study. The PI/Co-PI will be involved in clinical care and recommendations both during Phase 2 and Phase 3 (and beyond).
- 3) MS Physicians will be involved in initial identification of potential subjects and all MS-related continuity of care.
- 4) Falk Pharmacy serves UPMC for clinical trials, and staff will ensure the 1:1 randomization and distribution of either twenty placebo or biscodyl 10 mg rectal suppositories (used every other day over 4 weeks during the study period). Falk Pharmacy staff is experienced in running clinical trials and maintaining double-blind study conditions between subjects and investigators. Patients will receive a slight excess number of suppositories in order to assess study medication compliance at trial end.

STUDY MEASURES: We plan to obtain the following information from all enrolled patients:
1) Primary Patient-Reported Outcome Measure: "Using a scale of 1 to 10 (1 being no problem and 10 being maximally impactful symptoms), how would you rate the severity of your bowel symptoms over the past 2 weeks?"

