#### SECONDARY END POINTS:

1) Daily Bowel Diaries – patients will record the consistency (Bristol Stool Scale, 1-7), number of bowel movements (BM), and occurrence of any fecal incontinence (FI) episodes each day. This data will be used to abstract BM and FI weekly frequency, as well as the mean change in stool consistency during the study period.

- 2) Patient Assessment of Constipation Symptom Questionnaire (PAC-SYM)
- 3) Fecal Incontinence Severity Index (FISI)
- 4) Patient Assessment of Constipation QOL (PAC-QOL)
- 5) Rockwood Fecal Incontinence Quality of Life Scale (FIQL)
- 6) SF-36 health status questionnaire
- 7) Study Medication Compliance
- 8) Anorectal Sensory and High Resolution Anorectal Manometry Testing: First sensation of rectal filling, urgency, and pain, basal anal resting pressure, voluntary anal squeeze pressure, and the rectal-anal inhibitory reflex (RAIR) to rectal distention and simulated strain, as well as the ability to evacuate a 50 cc volume rectal balloon within one minute.
- 2.18 Describe the statistical approaches that will be used to analyze the study data.
  - \* Addressed below:

Categorical data will be analyzed using Fisher's Exact tests for differences in proportions. Continuous data will be analyzed using Student's t-tests to detect differences in group means, with Bonferroni correction for multiple comparisons. We will use logistic regression to determine the factors that predict treatment responses.

A p<0.05 will be used as the threshold for statistical significance in all cases.

POWER ANALYSIS/SAMPLE SIZE: It is generally regarded that a 3-point reduction represents a clinically meaningful change using such a 10 point scale, and similar research studies using patient-reported outcomes have reported standard deviations ranging around ~2.5 points. However, we do not have baseline data to estimate variance, and thus we took a conservative estimate with an expected standard deviation of 4 points. Given these assumptions, we will need 28 patients in each study arm to detect at least a 30% reduction in symptom severity, with a power of 0.80, alpha=P<0.05 in a two-tailed analysis.

[reviewer notes-]

- 2.19 Will this research be conducted in (a) a foreign country and/or (b) at a site (e.g., Navajo Nation) where the cultural background of the subject population differs substantially from that of Pittsburgh and its surrounding communities?
  - \* No

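### Aim 2 lets the baseline rating predict a response calculated from that same rating, so its raw association with response cannot be interpreted in either direction

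*Combined protocol and SAP*

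**What the plan says.** Section 1.2, Aim 2, lists what will be collected, starting with patients' "assessed severity of baseline and treatment-associated anorectal dysfunction", and continues: "All of these measures will be used to explore factors that are associated with treatment response". Aim 1 in the same section sets the outcome: "We will define an adequate treatment response as greater than a 30% reduction in symptom severity using an intention-to-treat analysis". The change is taken "at end of 4 weeks compared to baseline values"; 2.17 repeats the 30% criterion for the single 1-10 item, which is the first study measure in 2.6.

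For the baseline visit, 2.6 (Study flow) says only that "additional measures of baseline bowel symptom severity and bowel-related quality of life (QOL) will be obtained by standardized questionnaires". No second baseline rating is described.

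Section 2.18 gives the method in one sentence, "We will use logistic regression to determine the factors that predict treatment responses", and the threshold in another: "A p<0.05 will be used as the threshold for statistical significance in all cases". It lists no covariates, no arm term and no arm-by-baseline term. Nothing excludes the 1-10 rating from the predictors.

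**The concern.** If a patient happens to rate too high at Phase 1, the error raises the predictor and also raises the apparent fall from baseline. The two sides of the regression share an error, so an association can appear when severity has no bearing on who improves. Because the criterion is a percentage, a second effect pulls the other way: a patient with a low rating needs fewer points to cross the cut. The observed slope mixes the two in unknown proportion.

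Predicting who benefits is one of the trial's two aims, and the abstract repeats it. Baseline severity is the first candidate Aim 2 names. A statement that worse, or milder, patients respond better could be reported from a relation built into the definitions.

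**Working it through.** **Inputs from the documents.** Response is a fall of more than 30% from the baseline 1-10 rating (1.2, 2.17). One baseline rating is taken (2.6). The target is 70 patients with about 20% drop-out (2.6, 3.12). Withdrawals after Phase 1 count as non-response (5.16). The test level is 0.05.

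**Assumed inputs.** Baseline mean 6.5, SD 2.2, test-retest reliability 0.5 to 0.9. The documents give no reliability, and 3.12 says there are no baseline data on variance in this population.

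**The plan's own figure.** n per arm = 2 × (1.96 + 0.842)² × 4² / 3² = 2 × 7.85 × 16 / 9 = 27.9, so 28. Then 56 / 0.80 = 70. Both reproduce and are not in dispute; they fix the number of patients used below.

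**Step 1, algebra.** Let T be true severity, B = T + error the baseline rating, and F = (1 − f)T + error the week-4 rating when everyone truly falls by the fraction f. Let r be the reliability of B. Response means F < 0.7B. The expected F given B rises with slope (1 − f)r, so the margin 0.7B − E(F given B) has slope 0.7 − (1 − f)r.

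- f = 0.30: slope 0.7(1 − r), which is 0.35 at r = 0.5 and 0.07 at r = 0.9. It is positive for any imperfect rating.
- f = 0.20: zero at r = 0.7/0.8 = 0.875, negative above.
- f = 0.10: zero at r = 0.7/0.9 = 0.78.
- f = 0: zero at r = 0.70.

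The sign therefore depends on two unknowns, the reliability and the size of the fall.

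**Step 2, how often it reaches p<0.05.** Simulated integer ratings limited to 1-10, the same true fall in everyone, no arm difference. Entries are the percentage of trials in which the baseline rating is significant; the nominal rate is 5%.

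| Setting | r = 0.5 | 0.6 | 0.7 | 0.8 | 0.9 |
|---|---|---|---|---|---|
| 30% fall, complete follow-up | 65 | 57 | 34 | 20 | 8 |
| 30% fall, 14 of 70 (20%) set to non-response | 55 | 36 | 25 | 13 | 4 |
| 20% fall | | 28 | 14 | 4 | |
| No change | | 5 | 7 | 11 | |

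With 500 trials per setting the standard error is at most √(0.5 × 0.5 / 500) = 2.2 points. Repeat runs of the first row gave 65-70, 50-57, 34-42, 19-23 and 5-10. At r = 0.6 in that row, about 35% respond at baseline 3 and 72% at baseline 9. The 30% setting sits on the response cut and is unfavourable to the plan, but it is not a strict ceiling. With a uniform 40% fall the Step 1 slope at r = 0.6 is 0.7 − 0.6 × 0.6 = 0.34, against 0.7 − 0.7 × 0.6 = 0.28, and simulated rates were also higher.

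**Step 3, the reversal.** A separate simulation used mean 6, SD 2.5 and no change in any patient.

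| r | Responders, baseline ≥8 | Responders, baseline ≤5 | Odds ratio per observed point | Odds ratio per true point |
|---|---|---|---|---|
| 0.4 | 31% | 14% | 1.22 | 0.76 |
| 0.7 | 14% | 15% | 0.99 | 0.71 |
| 0.9 | 2% | 11% | 0.75 | 0.61 |

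At low reliability the error reverses the sign of the relation with true severity; near 0.7 it hides it; at high reliability the percentage arithmetic dominates. Whole-number ratings add unevenness: baseline 1 cannot respond, 2-3 need a 1-point fall, 4-6 need 2, 7-9 need 3 and 10 needs 4.

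**Step 4, adjusting for the rating instead of removing it.** Take another baseline questionnaire equally related to severity, with its own independent error, and the uniform 30% fall. With the 1-10 rating also in the responder model, the questionnaire falsely predicts worse response in 37% to 85% of trials across the reliability range. Without the rating the figure is roughly 6% to 17%. For a fixed B, a higher questionnaire score signals a higher T, hence a B that is too low, hence a smaller apparent fall.

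**Step 5, the arm-by-baseline term in a linear model of the week-4 rating.** With no arm difference it is significant in 3% to 6% of trials, because the shared error is the same in both arms. With a uniform 40% fall on active and 10% on placebo it is significant in 12% to 67%. An effect that is equal in percent is unequal in points.

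**The case against.** The strongest reply is that the size and direction rest on inputs the documents do not contain. That stands. A reader might infer that severe patients will look like better responders. The documents do not support this, because the direction needs low reliability or a sizeable fall, and Steps 1 and 3 show the opposite sign otherwise. Part of that opposite sign is a real property of a percentage criterion, not error.

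It can also be said that Aim 2 speaks of assessed severity without naming the 1-10 item, that PAC-SYM and FISI measure severity too, and that 2.18 lists no covariates. This stands as a limit: inclusion of the item is the natural reading of a sentence covering all measures, not an explicit statement. The coupling is exact only for that item. The other questionnaires inherit it only if their errors at the visit are correlated with those of the rating, which is not shown.

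Finally, Aim 2 is worded as exploration, and no rule for selecting patients is planned. A reader might infer that the efficacy result or a treatment rule is compromised. Neither follows. The randomised comparison in Aim 1 does not depend on this regression, and the plan presents the regimen as suitable for most patients. What the reply does not remove is the coupling itself, against which the plan has no safeguard.

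**Conclusion.** The point holds in a limited form. As planned, the raw association between the baseline 1-10 rating and response is uninterpretable in either direction, because one error-prone rating is both predictor and reference. In the assumed setting of a uniform 30% fall, a significant result appears in about 65% of trials at reliability 0.5 and 8% at 0.9. With smaller falls, or with drop-outs counted as non-response, it is less frequent, and at high reliability the sign can reverse. These figures rest on an assumed mean, SD, reliability and common percentage fall; the coupling follows from the plan's own definitions. The consequence is confined to an exploratory aim, so this is a matter of wording and analysis choice that should be settled before the data are examined.

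**What to change.** In Aim 2 and 2.18:

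1. Remove the baseline 1-10 rating from the candidate predictors of the >30% response, and do not report its main effect as a predictor.
2. Do not put it back in that responder model as an adjustment term, for the reason in Step 4.
3. Judge whether benefit depends on baseline severity from the arm-by-baseline-rating term in a model of the week-4 rating containing arm and baseline rating, labelled exploratory.
4. State that this term answers the question in points. A treatment effect that is the same percentage in every patient would also appear as an interaction, so a positive result should be checked on a proportional scale before any claim that severe patients benefit more.

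Removing the rating does not make the other severity questionnaires free of the percentage effect in Step 3, so their main effects should be described as raw associations.

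The cost is two or three sentences and one extra model, with no new data or visits. The sponsor gives up reporting the raw baseline-response association as a finding.
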